**Table 3 Incidence of CMV EOD, Death, aGVHD (Grade 3-4), cGVHD (High Risk) and a Composite of All Variables**

	ASP0113 (n=40)	Placebo (n=34)	P value
CMV EOD	3 (7.5%)	3 (8.8%)	1.000 §
Mortality	7 (17.5%)	11 (32.4%)	0.1775 §
aGVHD (grade 3-4) †	2 (5.0%)	5 (14.7%)	0.2364 §
cGVHD (high risk) ‡	4 (10.0%)	7 (20.6%)	0.3259 §
Composite	13 (32.5%)	18(52.9%)	0.0995 §

aGVHD: acute graft-versus-host disease; cGVHD: chronic GVHD; CMV: cytomegalovirus; EOD: end-organ disease

Per-protocol population: all unpaired recipients who met the inclusion/exclusion criteria and received at least 1 injection and had at least 1 post-transplant assessment relevant to an efficacy endpoint.

†Glucksberg et al, Transplantation 1974

‡Akpek et al, Blood 2003

§ Fisher's Exact Test

Further investigation of the phase 2 study results of the relationship between CMV viremia and potential phase 3 endpoints was investigated by Cox proportional hazards models using past or current viremia as a time-dependent covariate. Results of these analyses are summarized in [Table 4](#). Although incidence of each of these events is numerically greater among subjects who have had CMV viremia, the effect of CMV viremia is not statistically significant.

**Table 4 Results of Cox Proportional Hazards Models on the Effect of Past or Current CMV Viremia (defined as viral load > 1000 by central lab assay) on Endpoint Events**

Component	Events	Hazard Ratio	95% CI	P value
aGVHD (Grade 3-4)	7	1.13	0.20, 6.51	0.88
cGVHD (Severe)	11	1.27	0.39, 4.16	0.69
Severe Infection (CTCAE Grade 3-5)	48	1.72	0.84, 3.49	0.14

aGVHD: acute graft versus host disease; cGVHD: chronic graft versus host disease; CTCAE: common terminology criteria for adverse events; CMV: cytomegalovirus

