### **4.5 Assignment and Allocation**

At the screening visit, after the Informed Consent Form (ICF) has been signed, the subject will receive a subject number assignment through the IRT for use throughout the study.

Subjects who subsequently meet all inclusion and none of the exclusion criteria will be randomly assigned to receive either ASP0113 or placebo. The randomization to treatment will be equally allocated (i.e., 1:1) and stratified by donor-recipient relatedness and donor CMV serostatus. At least 30% of subjects enrolled will be donor-seronegative.

The IRT vendor will generate the randomization schedule. To obtain the randomized treatment assignment for a subject, the pharmacist or designee will utilize an IRT, which is available 7 days a week, 24 hours a day.

Randomization is to be done after the completion of the screening period, and at least -14 to -3 days prior to the anticipated transplant day (day 0). The first injection must be given within 72 hours prior to the start of conditioning therapy after randomization. After submitting required information about the eligible subject, the drug kit number assignment will be provided.

Study drug assignment will remain blinded to all site staff except the pharmacist and designated staff.

If a subject is randomized but does not receive study drug, the subject number will not be used again. In this instance, the treatment assignment should only be known by the pharmacist and designated staff (i.e., the blind must be maintained as it is with all other subjects).

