### **6.2 Discontinuation of the Study**

When the Sponsor is aware of information on matters concerning the quality and safety of the study drugs, as well as other important information that may affect proper conduct of the clinical study, the Sponsor may discontinue the clinical study and send a written notice of the discontinuation along with the reasons to the Investigator (for sites in Japan: to the head of the study site), and regulatory authorities.

The DMC is responsible for periodically reviewing select accruing data for the purpose of ensuring subject safety. The DMC is an independent multidisciplinary group consisting of

clinicians and a biostatistician external to Astellas that, collectively, has experience in the management of patients undergoing HCT and other diseases, and in the conduct and monitoring of randomized clinical trials with interim analyses.

The DMC statistician will perform a futility analysis on efficacy data for presentation to the DMC at selected DMC meetings. The futility of ASP0113 will be monitored based on its effect on viremia (defined as a CMV plasma viral load  $\geq 1000$  IU/mL as assessed by the central laboratory). It is believed that viremia is a surrogate of treatment effect on clinical endpoints. Subjects receiving ASP0113 had a statistically significant reduction in viremia relative to placebo in the phase 2 trial of ASP0113. Although there are no explicit safety stopping rules, all safety issues will be thoroughly evaluated by the DMC with special attention paid to local reactogenicity and hypersensitivity cases.

Futility analysis will be performed when the first 100 subjects have been randomized, and every 3 months thereafter until the total enrollment reaches 400 subjects. Futility analysis are based on the rate of CMV viremia defined as CMV plasma load  $\geq 1000$  IU/mL as assessed by the central laboratory. Analysis will include all available viremia data obtained from the central laboratory up to the time of a cut-off point for each futility analysis. At each futility analysis, a Bayesian posterior probability that the hazard ratio for viremia of the ASP0113 treatment group to the placebo treatment group will be less than 0.75 will be calculated.

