#### **7.4.3 Analysis of Other Variables**

The maximum grade of aGVHD, maximum cGVHD global score, number of episodes of protocol-defined CMV viremia, and duration of hospitalizations will each be tested using a Kruskal-Wallis test.

Incidence of overall mortality, CMV EOD, grade 3-4 aGVHD, severe cGVHD, grade 3 infections other than CMV, relapse mortality, non-relapse mortality, graft rejection, failure to engraft, and incidence of relapse of primary disease requiring therapy will each be tested using a stratified analysis of the binary response using a CMH test to account for the stratification variables used as part of the randomization. Subjects who discontinue the study without experiencing the event considered in the analysis will be considered as having the event for the statistical analysis.

Number of episodes of protocol-defined CMV viremia [CMV plasma viral load  $\geq 1000$  IU/mL by the Abbott RealTime CMV assay as assessed by the central laboratory] will be compared between treatments using the stratum-adjusted Kruskal-Wallis test, adjusting for donor-recipient relatedness and donor CMV status. To estimate the association between CMV viremia and mortality, a multivariable Cox proportional hazards model will be constructed in a time-dependent manner. The model will be adjusted for the factors used to stratify the randomization. CMV viremia will be treated as a time-dependent variable, starting at the time of the first occurrence of protocol-defined CMV viremia.

The maximum grade of aGVHD, maximum cGVHD global score, and duration of hospitalizations will each be tested using a stratum-adjusted Kruskal-Wallis test adjusting for donor-recipient relatedness and donor CMV serostatus.

The treatment effect on time to engraftment and time to platelet recovery will each be analyzed in a Cox proportional hazards model including the factors used to stratify the randomization.

Immunogenicity analysis will be conducted using the IAS. Descriptive statistics on the raw and log transformed results will be presented by treatment group and collection time point. The Wilcoxon rank sum test will be used to compare treatment groups at each of the time points for immunogenicity assessment for the following:

- Antibody response to gB antigen
- T cell response to viral protein pp65

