7.4.1.2 Additional Analyses of the Primary Efficacy Endpoint

Additionally, the primary efficacy endpoint will be further evaluated using a different method and different data source for the FAS and mFAS analysis sets.

Time to first occurrence of the primary endpoint event will be analyzed in a Cox proportional hazards model where the time to event will be calculated in days from transplant to the earliest component observed. Subjects not experiencing the primary endpoint event will be censored at the time of their last follow-up visit. The last day of follow up visit will be defined as last known day alive. If a subject's last known day alive is beyond day 380 and has no CMV EOD according to the adjudication committee, this subject will be censored on day 380. The Cox model will include treatment group, donor/recipient relatedness, donor serostatus (the stratification factors for randomization). Additionally, 1- hazard ratio and its 95% CI will be calculated.

Cumulative incidence functions (CIF) will be used to estimate the crude incidence of the primary endpoint by treatment group, and a Kaplan-Meier plot may also be considered.

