7.4.3.1 Analyses of Clinical Outcomes Exploratory Endpoints

The following exploratory endpoints will be analyzed by incidence and/or time to event approach by treatment group.

For the endpoint of adjudicated CMV EOD, and Investigator-reported CMV EOD, the summary will include incidence (i.e., number of episodes) where all events are added in addition to the number and percentage of subjects with at least one event. The proportion of subjects with an event will be analyzed by the CMH method and the odds ratio, its 95% CI and p-value will be calculated.

- Composite endpoint of all-cause mortality and adjudicated CMV EOD at 6 months post-transplant, using the same CMH approach as the primary endpoint. Deaths occurring up to day 180 from transplant will be counted. In other words deaths occurring on or before 180 days after transplant will be counted, although the death could be reported later. Patients with CMV EOD that is assessed by the independent and blinded adjudication committee will be counted for the events that are observed up to day 190 from transplantation.

- All-cause mortality at 6 months post-transplant using time to event method, as described in Section 7.4.1.2. Deaths occurring up to day 180 from transplant will be counted. In other words deaths occurring on or before 180 days after transplant will be counted, although the death could be reported later.
- Relapse mortality (death due to relapse of the subject's primary disease), using the same CMH approach as the primary endpoint.
- Non-relapse mortality (death due to causes unrelated to the subject's primary disease), using the same CMH approach as the primary endpoint.

The proportion and number of subjects the events below will be descriptively summarized.

- Proportion of grade 3-4 aGVHD
- Proportion of engraftment (Yes/No)
- Proportion of graft rejection/poor graft function
- Proportion of relapse of primary disease requiring therapy

Additionally, number (percentage) of subjects by taking the maximum grade of aGVHD will be summarized.

Karnofsky Performance Scale (KPS) scores are collected at baseline and post-baseline. KPS scores will be descriptively summarized at baseline and the visits specified in schedule of assessments (Table 1), but KPS scores at any additional visits will only be listed.

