7.4.3.1.1 Association of CMV Viremia and Mortality

To estimate the association between CMV viremia and mortality, subjects in each treatment group will be cross-tabulated by viremia or no viremia within 1 year post-transplant, and by alive or dead at 1 year post-transplant. In addition, a multivariable Cox proportional hazards model will be constructed in a time-dependent manner. The model will be adjusted for the factors used to stratify the randomization. CMV viremia will be treated as a time-dependent variable, starting at the time of the first occurrence of protocol-defined CMV viremia. The model for this analysis will include, in addition to CMV viremia, all the factors included in the final Cox regression model described earlier in this subsection.

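### The exploratory viremia–mortality Cox model has no usable covariate list: the Protocol adjusts only for the two randomization factors, and the SAP adds those of a model it never describes, so the hazard ratio is open to confounding

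*Protocol*

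**What the plan says.** Protocol 7.4.3 sets the aim and form of the model: "To estimate the association between CMV viremia and mortality, a multivariable Cox proportional hazards model will be constructed in a time-dependent manner". Viremia switches on at its first protocol-defined occurrence. On covariates the Protocol says only "The model will be adjusted for the factors used to stratify the randomization". Protocol 4.5 identifies those factors: randomization is "stratified by donor-recipient relatedness and donor CMV serostatus". Treatment is not named. The synopsis says the same.

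SAP 7.4.3.1.1 repeats the Protocol text, adds a cross-tabulation of viremia by vital status, and then says the model also includes "all the factors included in the final Cox regression model described earlier in this subsection". SAP 6.1.3 lists this association among the exploratory endpoints.

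SAP 7.4.3.1 sets out no Cox model or covariate list before that point, and no selection procedure in the SAP would produce a final model. The one route to a Cox model is a cross-reference for another endpoint: "All-cause mortality at 6 months post-transplant using time to event method, as described in Section 7.4.1.2". The model in SAP 7.4.1.2 holds treatment group and the two stratification factors.

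**The concern.** Adjusting for stratification factors suits a randomized comparison of arms. This model compares subjects who have become viremic with those who have not, and randomization does not balance those groups. A subject who is older, has more comorbidity or has had more intensive conditioning may be both likelier to become viremic and likelier to die. A hazard ratio above 1 can then appear with no effect of viremia on death.

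The second problem is execution. Two programmers working from SAP 7.4.3.1.1 could fit different models, and the choice could be made after unblinding.

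What is at stake is how the estimate is interpreted. Protocol 6.2 states "It is believed that viremia is a surrogate of treatment effect on clinical endpoints", and this is the planned within-trial look at viremia and death. A confounded hazard ratio could be taken as support for that belief.

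**Working it through.** **Plan's own figures.** The documents give no number for this model. The trial size used below does reproduce. For 35.3% versus 22.5%, two-sided 0.05 and 80% power, the uncorrected formula is n = [1.96·√(2·0.289·0.711) + 0.842·√(0.353·0.647 + 0.225·0.775)]² / 0.128², which gives 196 per arm. With the continuity correction named in SAP 4, it gives 212 per arm, or 424 in total. At 250 per arm the corrected power is 86.6%, against 86% stated.

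**What the text allows.**

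| Source | Covariates besides viremia |
|---|---|
| Protocol 7.4.3 | relatedness, donor serostatus |
| SAP 7.4.3.1.1 | the same, plus an undefined set |
| SAP 7.4.1.2 (nearest candidate) | the same, plus treatment |

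**Simulation inputs.**
- From the plan: N = 500, allocated 1:1.
- Death by 1 year: 28% assumed, between the phase 2 arm figures of 20.8% and 32.6% (Protocol 1.3.2.2). This gives 500 × 0.28 = 140 deaths.
- Viremia: 50% assumed, between the phase 2 central-laboratory rates of 33% and 62%, which used a different assay threshold. Onset falls on days 14 to 100; Protocol 2.2.2 expects first episodes near day 30.
- Vaccine hazard ratio on viremia: 0.6 (assumed).
- True viremia–death hazard ratio: 1.
- One binary baseline factor with 40% prevalence, multiplying both hazards by assumed amounts.

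Start-stop Cox models were fitted in 600 simulated trials per scenario. False harm means z > 1.96, nominally 2.5%.

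| Factor's HR on viremia / death | Strata only: HR, false harm | Strata + treatment: HR, false harm | Strata + factor: HR, false harm |
|---|---|---|---|
| 1 / 1 | 1.00, 3.5% | 1.00, 3.8% | 1.00, 3.3% |
| 1.5 / 1.5 | 1.06, 4.8% | 1.06, 4.2% | 1.00, 1.8% |
| 2 / 2 | 1.17, 14.3% | 1.17, 14.5% | 1.00, 3.0% |
| 2 / 3 | 1.28, 25.8% | 1.29, 26.2% | 1.00, 3.0% |
| 3 / 3 | 1.46, 56.5% | 1.48, 57.5% | 1.00, 4.0% |

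The Monte Carlo standard error, √[p(1−p)/600], runs from about 0.5 to 2 percentage points, so 4.8% against 3.5% is within noise.

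**Hand check.** If viremia has no effect, the crude hazard ratio is about [1 + p₁(h−1)] / [1 + p₀(h−1)]. Here h is the factor's hazard ratio on death, and p₁ and p₀ are its prevalence among viremic and non-viremic subjects. This ignores deaths before viremia onset. At 2/2, a cumulative viremia hazard of 0.662 in placebo non-carriers gives 50% viremic overall:
- Carriers: the mean of 1 − exp(−2·0.662) = 0.734 and 1 − exp(−2·0.6·0.662) = 0.548 is 0.641.
- Non-carriers: the mean of 0.484 and 0.328 is 0.406.
- p₁ = 0.4·0.641 / (0.4·0.641 + 0.6·0.406) = 0.513.
- p₀ = 0.4·0.359 / (0.4·0.359 + 0.6·0.594) = 0.287.
- Ratio = 1.513 / 1.287 = 1.18, against 1.17 simulated.

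The same steps give 1.233/1.167 = 1.06 at 1.5/1.5 (p₁ = 0.466, p₀ = 0.334) and 2.152/1.448 = 1.49 at 3/3 (p₁ = 0.576, p₀ = 0.224), against 1.06 and 1.46 simulated.

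**The case against.** The strongest reply is that little depends on this analysis. It is exploratory, both documents call its target an association, and an association that arises from shared frailty is still a true association. That stands. It limits the importance of the point and rules out any claim that a trial decision is compromised. It does not supply the missing covariate list.

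The confounder strengths are also assumed. At 1.5/1.5 the shift is small, and excluding modified HCT-CI scores of 4 or more (Protocol 3.3) narrows the comorbidity range. That stands too. The simulation shows what could happen and does not estimate what will.

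The clean 1.00 after adjustment arises because the simulated factor is fully measured at baseline. Real immune suppression changes after transplant, and Protocol 1.1 links GVHD to both CMV and survival. Baseline adjustment will therefore reduce confounding but may not remove it.

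A reader might infer three stronger things that the documents do not support:
- *That the SAP definitely adjusts for the two factors alone.* This is exact for the Protocol. In the SAP the set is undefined, and on the 7.4.1.2 reading treatment is included.
- *That a confounded estimate would feed the futility rule.* Protocol 6.2 and 7.9 base futility on the randomized between-arm hazard ratio for viremia, using the posterior probability that it is below 0.75. The viremia–death hazard ratio does not enter, and neither document says it will be used to validate surrogacy.
- *That the phase 2 hazard ratios in Protocol Table 4 (1.13 to 1.72) show bias of this size.* Those are for acute GVHD, chronic GVHD and severe infection, on 7, 11 and 48 events. None is for mortality, and the Protocol itself says "the effect of CMV viremia is not statistically significant".

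**Conclusion.** The point holds as a specification gap in one exploratory analysis. The Protocol's adjustment set is too thin for a non-randomized exposure. The SAP's set cannot be executed as written, and its most generous reading adds only treatment, which leaves the bias unchanged (1.17 with or without treatment at 2/2).

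With no true effect, one omitted factor of 40% prevalence moves the hazard ratio to about 1.06, 1.17 or 1.46 when it multiplies both hazards by 1.5, 2 or 3. The bias is negligible at the first of these and material from the second. These figures rest on the assumed prevalence, strengths, viremia rate and death rate; the documents give no values for the omitted factors.

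The primary, key secondary and futility analyses are not affected. The correction is worth making before unblinding because it costs little and removes an open choice.

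**What to change.** In SAP 7.4.3.1.1:

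1. Delete the reference to the earlier Cox model.
2. Before unblinding, fix the covariates as time-dependent viremia, treatment, donor-recipient relatedness, donor CMV serostatus, age (continuous), modified HCT-CI, baseline Karnofsky score, primary disease (AML or other), conditioning intensity and ATG use.
3. Report this model beside the strata-only model, which keeps the Protocol's analysis in view and shows how far adjustment moves the estimate.
4. State that time-varying GVHD is left out of the main model because it may be a mediator as well as a confounder.
5. State that the hazard ratio is an observational association with possible residual confounding and is not evidence of surrogacy.

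The cost is SAP wording and a few more model terms. The data are already planned: Protocol 5.2.1 (date of birth), 5.2.2 (disease status and conditioning), 5.2.4 (modified HCT-CI) and 5.3.2 (Karnofsky), with ATG use and conditioning intensity taken from the eCRF under SAP 7.2.3. The list has 10 terms, so about 140 deaths give 140/10 = 14 deaths per term.

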## **7.5 Analysis of Safety**

The SAF will consist of all randomized subjects who have at least 1 study drug injection. This analysis set will be used for all summaries and analysis of AEs, reactogenicity, clinical laboratory data, PEs, vital signs, and subject survival through 1 year post first study drug injection. All recorded AEs will be listed, including duration, outcome, toxicity grade, and association with use of study drug. In addition, the toxicity of antiviral therapy will be identified from its association with those products.

All AEs and SAEs will be collected from signing of the ICF through 30 days post last dose of study drug. All events requiring adjudication, Grade 3 and higher AEs and SAEs will be collected from 31 days post last dose of drug through 1 year post-transplant. AEs and SAEs are to be reported as a change in medical status or medical history from time of signing of informed consent through first dose of study drug. In this study, the day 0 HCT is not considered an AE.

TEAEs will be defined as those that occurred after the first dose of study drug and within 30 days of the last dose of study drug.

The coding dictionary for this study will be MedDRA. It will be used to summarize AEs by system organ class and preferred term.

Tables will include the following details:

- Number of TEAEs
- Number and percentage of subjects with TEAEs
- Number and percentage of subjects with drug related TEAEs
- Number of serious TEAEs

- Number and percentage of subjects with serious TEAEs
- Number and percentage of subjects with TEAEs by NCI-CTCAE Version 4.03 scale. AEs will be summarized by their worst CTCAE grade
- TEAEs that are deemed by the Investigator as local reactogenicity will be graded and summarized by their worst grade. The grading will be done using both the NCI-CTCAE Version 4.03 grading scale and in accordance with the FDA's Guidance for Industry: Toxicity Grading Scale for Healthy Adult and Adolescent Volunteers Enrolled in Preventive Vaccine Clinical Trials [Appendix 7](#)
- Number of deaths

## 7.6 Analysis of Pharmacokinetics

Pharmacokinetics will not be analyzed in this study.

## 7.7 Analysis of Pharmacogenomics

Samples will be collected and stored as described in [Appendix 19](#), Pharmacogenomics Sub-study, for potential retrospective analysis.

## 7.8 Protocol Deviations and Other Analysis

Protocol deviations as defined in [Section 8.1.6](#) will be summarized for all randomized subjects by treatment group and total as well as by site. A data listing will be provided by site and subject.

The protocol deviation criteria will be uniquely identified in the summary table and listing. The unique identifiers will be as follows:

- PD1- Entered into the study even though they did not satisfy entry criteria,
- PD2- Developed withdrawal criteria during the study and was not withdrawn,
- PD3- Received wrong treatment or incorrect dose,
- PD4- Received excluded concomitant treatment.

